8	P0									P1	SV								P2	FA					P3	FA								
9	P0									FI	P1	SV								P2	FA	FI				P3	FA							
10	P0										P1	SV								P2	FA					Р3	FA							
11	P0											P1	SV								P2	FA					P3	FA						
12	P0											P1	SV								P2	FA					P3	FA						
13	P0											FI	P1	SV								P2	FA	FI				P3	FA					
14	P0												P1	SV								P2	FA					P3	FA					
15	P0													P1	SV								P2	FA					P3	FA				
16	P0													P1	SV								P2	FA					P3	FA				
17	P0													FI	P1	SV								P2	FA	FI				P3	FA			
18	P0														P1	SV								P2	FA					P3	FA			
19	P0															P1	SV								P2	FA					P3	FA		
20	P0															P1	SV								P2	FA					P3	FA		
21	P0															FI	P1	SV								P2	FA	FI				P3	FA	
22	P0																P1	SV								P2	FA					P3	FA	
23	P0																	P1	SV								P2	FA					P3	FA
24	P0																	P1	SV								P2	FA					P3	FA

PO: Baseline measurement

SV: Site visit

P1: Measurement before site visit

P2: Measurement 8 months after the site visit

P3: Measurement 14 months after the site visit

FA: Follow-up audit

FI: Focus group interviews

Study population and intervention

Table 2. Key elements of the intervention

Time in months	Activity
1	Inspection team announces inspection and requests the hospital to submit information.
2	Inspection team reviews records of patients with sepsis and collect relevant data for the inspection criteria. Data is collected for two time periods, baseline (September 2015) and right before the site visit. Inspection team reviews information from hospital and prepares for the site visit.
3	Two day site visit at the hospital with interviews of key personnel. At the end of the site visit the inspection team presents the preliminary findings, and the hospital can comment on these preliminary findings.
4-5	The inspection team writes a preliminary report of their findings. The hospital can comment on the report.
6	The inspection team sends the final report to the hospital.
Continuously	The hospital plans and implements improvement measures.
11	Follow-up audit 8 months after the site visit. The inspection team reviews records of patients with sepsis and collect the same data as they did prior to the site visit. Report on findings from audit
17	Follow-up audit 14 months after the site visit. The inspection team reviews records of patients with sepsis and collect the same data as they did prior to the site visit. Report on findings from audit

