If the inspection reveals non-compliant performance, hospital management is responsible for planning and implementing necessary improvements. The inspection teams follow up the hospitals to confirm that necessary changes have been implemented and that the changes in fact improve clinical care. At 8 and 14 months after the inspections, the inspection teams conduct a follow-up audit where they review patient records and collect the same data that they collected prior to the inspection. These data provide insight into how the diagnostic and treatment processes for patients with sepsis are carried out, and is used to judge whether the hospital has managed to improve sepsis detection and treatment. Following the audits at 8 and 14 months, the inspection teams write a short report summarizing the initial findings of the inspection, what the hospital has done to improve their performance and the findings from the audit.

To reduce variation in the delivery of inspections, the Norwegian Board of Health Supervision has developed a common framework standardizing intervention delivery. All audit criteria and the way in which these should be measured are operationalized and described, and a detailed description of how the inspection teams should carry out the inspections is provided. Such a framework can contribute to harmonization of the inspection teams with regard to the way in which key activities are performed.⁵² The inspection teams also receive training and exchange experiences, to harmonize the way in which they deliver the intervention.

Data collection

Quantitative data

Figure 2 outlines the clusters and the data collection. For each inspection, we collect data at four different time points, referred to as P0, P1, P2, and P3. P0 is the baseline measurement for all hospitals before the Norwegian Board of Health Supervision announced the inspection campaign. The campaign is part of the regular planned inspection activities. These activities are transparent for the hospitals and are announced in advance, in this particular case six months before the first inspection. Due to practical reasons, the inspection teams collect data for P0 and P1 at the same time right before the inspection. Data for P0 are thus collected retrospectively, but it is pre-defined that the patients that will be included are the last patients with suspected sepsis that were admitted prior to October 1st 2015.

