We consider the percentage of patients with organ dysfunction who have received antibiotic treatment within one hour as the key measure, because it is associated with our outcome measure, 30-day mortality rate.^{27 28} Furthermore, we suggest that early triage and early assessment by medical doctor are key activities to secure timely treatment with antibiotics, and that the corresponding process measures consequently are important too.

The power calculations were performed using the *steppedwedge* function in Stata/IC version 14.0 (StataCorp LLC, College Station, TX, USA) software for Windows, developed by Hemming and Girling.⁵⁹ The statistical power in a stepped wedge design depends on the total number of intervention sites, the total number of data collection points for each intervention site, the number of patient records included at each data collection point, the correlation between clustered observations on the same hospital (intra-cluster correlation), and the implementation period.⁴⁵ We based our calculations on 24 intervention sites, 4 data collection points, and 33 patient records per

collection point at each intervention site. As the intra-cluster correlation may vary between samples and between process and outcome measurements, it is not straightforward to specify an intracluster correlation in advanced. In addition, we could not find any estimated intra-cluster correlation in previous trials of patients with sepsis. Consequently, we chose an intra-cluster correlation of 0.05, which is in line with that estimated for several patient outcomes in a cluster randomized trials of heart failure patients.⁶⁰ Type I and II errors were assumed to be 0.05 and 0.20, respectively.

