Because assessment of patient records must be done manually, data collection is resource demanding. Thus, we must balance the design and power of the study against the available resources, a manageable amount of data collection, and likely detectable changes in the key effect measures. For the process data, we have powered the study according to the key clinical process indicator, antibiotic treatment within 1 hour of arrival at the hospital. To detect an absolute improvement of 15 percentage points, e.g., from 50% to 65% of patients receive antibiotic treatment within 1 hour of 2376 patient records. We intend to include n=3168 patients (24 hospitals × 4 time points × 33 patients); we assert that this sample is large enough to examine the other relevant process indicators described in box 3.

To reach sufficient statistical power to detect a significant change in patient outcome measures, such as 30-day mortality rate, we need to include more than the 33 patients that we include to detect changes in process measures per each time point. We have powered the study to detect a reduction from 15% to 11.5% in the mortality rate by including 60 patients for each hospital at each time point. The total intended number of included patients for outcome measures is n = 5760 patients (24 hospitals × 4 time points × 60 patients).

Qualitative data

We conduct focus group interviews based on an interview guide. We developed the interview guide based on theory about practices involved in implementing organizational change⁶¹ along with our model for how inspections can contribute to improving quality of care by affecting organizational change activities and ideas.³⁹ The key research questions that will be further explored in the qualitative study are displayed in box 4.

- How do inspection teams plan, conduct, follow up, and finalize the inspections?
- How do the inspected organizations prepare for inspections?
- Do inspections contribute to creating awareness about current performance and possible performance gaps in the clinical system for delivering care to patients with sepsis?
- Do inspections contribute to engaging leaders and clinicians in improvement of their work?
- Do hospitals initiate improvement activities aimed at enhancing the quality of sepsis care prior to inspections?
- Do inspections affect organizational ideas, e.g., understanding of the clinical system and

commitment to change?

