Descriptive statistics will be used to quantify sample characteristics. All analysis will use patient-level data, collected at four periods for different patients for 24 hospitals – two collections during the control period and two collections during the intervention period for each hospital. In order to compare the various process and outcome measurements (dependent variables) between the intervention and control periods (independent variable), we will use logistic regression models for binary measurements and linear regression models for continuous measurements. The choices of regression methods for the various measurements are outlined in table 3. As recommended in literature, ^{63 64} all models will include time as a covariate to adjust for potential secular changes in the

process and outcome measurements during the study period. The underlying form of time will be included in the models as a linear term, polynomial term, or cubic spline term, as appropriate.

Norway is divided into 18 counties in addition to its capital city, and there are acute hospitals that treat patients with sepsis in all counties. The population density varies between the counties. The smallest acute hospitals serve a population of about 50 000, while the largest serve a population of about 500 000. The sizes of the ICU units and the number of patients with sepsis treated during a year will therefore differ between the included hospitals. This is a national inspection campaign, and hospital in all counties will be inspected. As patients are sampled from different hospitals, a between-hospital variation in measurements is likely, introducing correlated data within the hospitals. To account for this intra-cluster correlation, we will use generalized estimating equations methodology,⁶⁵ specifying an exchangeable working correlation structure, i.e., any two patients are equally correlated within hospitals regardless of time and intervention and control periods. However, as this assumption might not hold for all hospitals, a method for obtaining cluster-robust standard errors of model parameters will be applied.⁶⁶ Finally, as our repeated sampling of patients with sepsis may not be entirely representative of the total population, difference in certain patient characteristics, including age and sex, between comparison periods might arise. In that case, the abovementioned models will also include such covariates for obtaining correct model means.

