The patients included in this study have a suspected serious infection that potentially requires rapid treatment. The process data that we collect addresses sepsis detection and treatment in the initial phase of the hospital stay, e.g., the time to triage, assessment by a physician, and antibiotics treatment. Such process measures are still relevant for the patient population included in our study, regardless of whether they fulfill the criteria for sepsis using the new definition. Because our main objective is to track changes over time in the quality of care delivered to a defined patient population, we assert that our study design and process data are still valid and relevant despite the introduction of a new definition of sepsis.

We had to balance the power of the study against the available resources and a manageable amount of data collection. We designed and powered the study to detect realistic changes in our outcome and process measures. However, there is an inherent risk that the study can become underpowered to detect changes in our effect measures. A potential challenge is information missing in the patient records. Lack of documentation itself can be an important finding because this can be associated with poorer patient outcomes.⁷⁷ If information regarding process measures is missing in the patient records, it will affect the power of the study, which can potentially become underpowered. If there is an association between substandard care and lack of documentation in the patient records, our pre-inspection data may be biased. Poor care will only be indicated by missing data but will not be supported by actual empirical data. Following inspection, it may be easier to improve the documentation practice within a hospital than actually improving the delivery of care. Thus, there is a risk that the post-intervention data will be biased because they include substandard care that would not have been documented prior to inspection.

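### The 80% power implied for a mortality fall from 15% to 11.5% is not delivered: with the planned time adjustment on the Table 1 schedule, two-sided power is about 25% to 49%.

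*Combined protocol and SAP*

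**What the plan says.** The power calculations are in the Quantitative data part of Data collection. They name the Stata stepped-wedge routine, 24 sites, four collection points and an intra-cluster correlation (ICC) of 0.05. They add: "Type I and II errors were assumed to be 0.05 and 0.20, respectively". For mortality the text then says: "We have powered the study to detect a reduction from 15% to 11.5% in the mortality rate by including 60 patients for each hospital". That number applies to all four collections, 5760 patients in all. The text gives neither the sidedness of the test nor the number of steps and treatment of empty cells entered in the software.

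On the model, the Statistical analysis section says that "all models will include time as a covariate to adjust for potential secular changes", and: "The underlying form of time will be included in the models as a linear term, polynomial term, or cubic spline term, as appropriate". The method is GEE with exchangeable working correlation and cluster-robust standard errors.

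On the schedule, P0 is fixed for all hospitals as "the last patients with suspected sepsis that were admitted prior to October 1st 2015". Table 1 places P1 in the month before the site visit, and its key reads "P2: Measurement 8 months after the site visit" and, for P3, 14 months. P0 and P1 are control data; P2 and P3 are inspected data.

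The limitations section says that "there is an inherent risk that the study can become underpowered to detect changes in our effect measures". It gives no lower power figure.

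**The concern.** Every hospital passes through control, control, inspected, inspected in the same order, and the inspections are spread over only 12 months. Inspected status is therefore close to a function of calendar time. A model that adjusts for time, as this plan requires, must estimate the effect from the little that is left, and 60 patients per cell may be far too few.

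This matters because the protocol calls 30-day mortality its key outcome measure, and it serves the third objective. A reader told that the study was powered for a 3.5-point fall could take a null result as evidence that inspections do not reduce mortality. The limitations section invites that reading: it attributes absence of change to weak delivery of the inspection or to the hospital's lack of capacity for improvement, and does not mention low power there.

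**Working it through.** **Inputs.** From the power text: p0 = 0.15, p1 = 0.115, difference 0.035, m = 60 per hospital per point, 24 hospitals, ICC = 0.05, α = 0.05. Assumed here: a two-sided test, a constant effect, no decay of correlation over time, and Table 1 months as printed. Average binomial variance: (0.15×0.85 + 0.115×0.885)/2 = 0.1146.

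**Can the plan's figure be reproduced?** Take a textbook wedge with four periods, three steps and eight hospitals per step (5760 patients). The standard stepped-wedge variance is

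v = Iσ²(σ² + Tτ²) / [(IU − W)σ² + (U² + ITU − TW − IV)τ²],

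with I = 24, T = 4, U = 48, W = 896, V = 112, σ² = 0.95×0.1146/60 = 0.001815 and τ² = 0.05×0.1146 = 0.00573. This gives v = 0.000261, SE = 0.0161, and power 58% two-sided or 70% one-sided. Other layouts:

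- Six steps with 60 patients in all seven periods: 86%, but this needs 10,080 patients.
- Four steps, one-sided: 81%, but this needs five periods and 7200 patients.

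None of these layouts gives 80% with four points and 5760 patients.

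**The Table 1 schedule.** Counting September 2015 as month 1:

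- P0 = month 1 for all hospitals.
- P1 = months 7 to 18 (March 2016 to February 2017), two hospitals per month.
- P2 = P1 + 9 (December 2016 to November 2017).
- P3 = P1 + 15 (June 2017 to May 2018).

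Control and inspected data share months 16 to 18 only, which is 12 of the 96 hospital-period cells. Inspected status and month correlate at 0.85 over all cells and at 0.88 within hospitals.

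**Hand check.** Without a time term the effect is a within-hospital contrast of two cells against two: SE² = (0.95×0.1146/60)(1/2 + 1/2)/24 = 0.0000756, so SE = 0.0087. Adjusting for linear time within hospitals multiplies the variance by about 1/(1 − 0.879²) = 4.4, so SE is about 0.018.

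**Full calculation.** Generalised least squares on the 96 cell means with a hospital random intercept: SE² is the effect element of (Σ D′V⁻¹D)⁻¹, power = Φ(0.035/SE − 1.96), and the detectable difference at 80% power is (1.96 + 0.84)×SE.

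| Time term | SE | Variance ratio to no time | Power, two-sided | Power, one-sided | Detectable at 80% (two-sided) |
|---|---|---|---|---|---|
| None (not allowed by the plan) | 0.0087 | 1 | 98% | 99% | 2.4 points |
| Linear | 0.0181 | 4.3 | 49% | 62% | 5.1 |
| Quadratic | 0.0190 | 4.8 | 45% | 58% | 5.3 |
| Cubic | 0.0254 | 8.5 | 28% | 40% | 7.1 |
| Four-knot spline | 0.0266 | 9.3 | 26% | 37% | 7.4 |
| Fifth-degree polynomial | 0.0270 | 9.6 | 25% | 36% | 7.6 |

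A three-knot spline behaves like the quadratic (about 45%).

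**Patients needed for two-sided 80% on this schedule.** Linear: 127 per cell, 24×4×127 = 12,192. Cubic: 257 per cell, 24,672.

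**Sensitivity.**

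- ICC from 0.001 to 0.20: 49% to 56% (linear), 28% to 36% (cubic).
- Most generous case tried (ICC near 0, variance at 11.5% throughout, linear time): 59% two-sided, 71% one-sided.
- Between-period correlation decaying by an assumed ratio of 0.8: 33% (linear), 20% (cubic).

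**Simulation of the planned analysis** (logistic GEE, exchangeable, robust SE, z test). One set of 600 runs gave 54% (linear), 45% (quadratic) and 31% (cubic). With a t reference on 22 df these became 49%, 42% and 28%. A second, separate set of about 930 to 1120 runs per setting gave 49% (linear) and 28% (cubic). False-positive rates with the z test were about 6% (linear) and 9% to 10% (cubic), so the z-test powers are if anything flattering.

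**The case against.** Several points can fairly be made for the plan.

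- The figure of 80% is not printed beside the mortality target. This is true, but the type II error of 0.20 is the only one given for the power calculations, and the statement that the study is powered has no other stated meaning.
- The range depends on choices the plan leaves open. The lower end needs a high-degree polynomial or a spline with four or more knots, and one simulation put linear time at 54%. A fair short summary is about one half with linear time and about 30% or less with cubic or more flexible forms. Neither approaches 80%.
- Table 1 is illustrative; slots are about seven weeks and monthly numbers may vary. Six seven-week slots give 45% (linear) and 23% (cubic), so this does not help.
- Planned covariates such as age, sex, organ dysfunction and hospital size could remove variance. A 10% to 20% reduction lifts linear-time power only to about 53% to 58%; about half the variance would have to go.
- The limitations section already warns of low power. The warning is general, gives no figure, and goes on to missing documentation. The shortfall here exists with complete records.
- On the Table 1 schedule, data collection ended by June 2018, so the sample cannot change, and the reported interval will show the precision. This limits the remedy to wording; it does not make the power statement correct.

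**Conclusion.** The concern holds. Under the protocol's own inputs, its Table 1 schedule and any of the listed time terms examined, the study does not have 80% power for a mortality fall from 15% to 11.5%. At that effect the chance of a significant result is about one in two with linear time and about one in four with cubic or more flexible time. The expected 95% confidence interval half-width is 1.96×0.0181 = 3.5 points (linear) to 1.96×0.0254 = 5.0 points (cubic), so even an estimate of zero would not clearly exclude the target effect.

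The exact percentages rest on the assumptions listed in the working, and the spline figures also on knots that the plan does not give. The conclusion does not: no listed time form reached 80% under any assumption tried. It concerns mortality only; the antibiotic target is not in question.

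**What to change.** Replace the mortality power sentence, or annotate it with a dated note, since the document was last updated in November 2021, after the Table 1 schedule ends.

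1. State the difference detectable at 80% power under the Table 1 design matrix and the planned model: about 5 points with linear or quadratic time, about 7 to 7.5 points with cubic or four-knot spline time.
2. State the sidedness of the test and the settings entered in the software.

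Two further changes are secondary but worth making at the same time.

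3. Fix one form of calendar time for the mortality model, because the choice within the listed forms moves the standard error from about 0.018 to 0.027.
4. State that a non-significant mortality result will be reported as inconclusive, with its confidence interval, and not as evidence of no effect.

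The cost is wording and one rerun of the power calculation. The stated figure becomes less favourable. No further patients or records are needed.

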The intervention will be rolled out sequentially during 12 months to 24 hospitals, with six clusters of four geographically close hospitals. Inspections are carried out by six regional teams with members from different County Governors and external clinical experts. Each team conducts four inspections in their region, yielding 24 inspected hospitals. Owing to practical and administrative implications, and general work planning for the involved team members, the four inspections must be clustered together and conducted within a limited time span. Each regional team is assigned a time slot of about seven weeks in which to conduct their inspections; the order of these time slots is randomized (random order generated by computer). Table 1 illustrates the incomplete stepped wedge design used in the study. The design is incomplete in that we do not continuously collect data from all the included sites, rather we collect data at four different time points. The inspections are rolled out successively over one year. On average, there are two inspections each month, though the exact number of inspections each month may vary due to practical work planning for the inspection teams and the involved hospitals.

To answer our research questions, we also need to collect qualitative data. We use focus group interviews to collect qualitative data. The phenomenon that we intend to study is how external inspections affect organizational change processes. Organizational change is dependent on interaction between individuals and groups in the organization.⁴⁷ Focus groups enable interaction between group members during data collection, thus resembling the phenomenon we wish to study. An inspection at a hospital represents one case, and for each case we conduct focus group interviews with the inspection team, leaders in the inspected hospital, and clinicians before and after the inspections.

Table 1. Study design

Year	2015				2016												2017												2018					
Hospital/	S	0	Ν	D	J	F	Μ	Α	М	J	J	Α	S	0	Ν	D	J	F	Μ	Α	Μ	J	J	Α	S	0	Ν	D	J	F	Μ	Α	Μ	J
month																																		
1	P0					FI	P1	SV								P2	FA	FI				Р3	FA											
2	P0						P1	SV								P2	FA					P3	FA											
3	P0							P1	SV								P2	FA					P3	FA										
4	P0							P1	SV								P2	FA					P3	FA										
5	P0							FI	P1	SV								P2	FA	FI				P3	FA									
6	P0								P1	SV								P2	FA					P3	FA									
7	P0									P1	SV								P2	FA					P3	FA								

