The stepped wedge design enables us to track changes in outcome measures for sepsis detection and treatment over time. The changes that we might observe in the outcome measures are not necessarily attributable to the inspections alone. There can be other factors beside the inspections that can affect sepsis detection and treatment during the study period. Our qualitative data can help identifying such factors and provide insight into how they might interact with the inspections. By combining findings from the qualitative and quantitative data, we assert that we can assess how sepsis detection and treatment develops over time and substantiate how inspections along with other factors can affect the development.

Our study is based on an overall framework suggesting that the inspections need to affect organizational ideas and activities to facilitate change in organizational behavior and thereby improve quality of care for patients with sepsis (figure 1). Moreover, we have developed a more detailed theory of change for the inspections, suggesting how they can contribute to affect organizational change. We collect quantitative data that indicate whether organizational behavior and the quality of care improve after the inspections. By combining these findings with our qualitative data that provide insight into how the inspections affect organizational change, we can test our theories about how inspections can contribute to improve the quality of care. We suggest that our study can contribute to build theory about how inspections can improve the quality of care, and thus have relevance for inspections covering other topics.

Initially, we had intended to use data from the NPR to calculate the 30-day mortality rate and hospital length of stay. After we had begun planning our study and had received ethical approval, a new definition for sepsis and septic shock was issued.⁷⁴ Patients with sepsis are identified in the NPR using diagnosis codes of the International Classification of Diseases, 10th revision (ICD-10). Previous research has shown that coding practice for sepsis varies between hospitals and can change over time.^{75 76} We assert that the new sepsis definition will affect how Norwegian hospitals code sepsis; therefore, we cannot use available routine data to calculate our outcome measures. Instead, we must use a more labor-intensive approach and manually scan all patient records that we include.

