The size of the included hospitals differ. The order of the inspections are randomized in clusters of four hospitals, and all the clusters include hospitals with different sizes. To account for intra-cluster correlation, we will use generalized estimating equations methodology,⁶⁵ and we will include hospital size as a covariate in our analytic models. Due to Norwegian topography with long travel distances, patients with suspected sepsis are typically sent to the nearest acute hospital for initial diagnosis and treatment. In some cases patients with septic shock can be transferred to a larger hospital later. We know the number of patients with organ dysfunction admitted to the various hospitals, and can adjust for this in our analysis. We do however not have access to data about comorbidity for the included patients and can therefore not fully adjust for case mix differences between the included hospitals. Our process measures cover the initial steps of the diagnostic and treatment process, which is done in all hospitals irrespectively of size. We compare changes in the effect measures before and after the intervention, and the intervention itself should not affect which patients that are admitted to the different hospitals. Consequently, we have no reason to believe that case mix differences between the inspected hospitals should change before and after the intervention.

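### Six team slots are randomised, but inference rests on 24 hospitals with no stated small-sample method and no analysis by the randomised groups

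*Combined protocol and SAP*

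**What the plan says.** The Study design section describes 24 hospitals "with six clusters of four geographically close hospitals", with the order of the six team slots drawn by computer. The section on strengths, limitations and biases repeats this: "The order of the inspections are randomized in clusters of four hospitals".

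The power calculation, under Data collection, uses the other unit. It defines intra-cluster correlation for patients of the same hospital, sets it at 0.05, and states: "We based our calculations on 24 intervention sites, 4 data collection points".

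The Statistical analysis section follows the hospital unit. It fits generalized estimating equations (GEE), "specifying an exchangeable working correlation structure, i.e., any two patients are equally correlated within hospitals regardless of time". Because that assumption may fail for some hospitals, "a method for obtaining cluster-robust standard errors of model parameters will be applied"; the method is given only by citation. Time may enter as a linear, polynomial or cubic spline term.

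No section gives a small-sample correction, a t reference, degrees of freedom, a team term, a team-level analysis or a randomisation-based test. The limitations section concedes: "There can be other factors beside the inspections that can affect sepsis detection and treatment during the study period".

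**The concern.** There are two separate issues.

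**Few clusters.** An uncorrected sandwich variance from 24 clusters is too small on average, and a z reference ignores the uncertainty in it. The test then rejects a true null too often, whatever the correlation structure.

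**Level.** A sandwich clustered on hospital treats hospitals as independent. If the four hospitals of a team move together in a given period, for reasons other than inspection, that shared movement is not counted. No hospital-level correction supplies it. A stable difference between teams is not the problem, because it largely cancels in the before/after contrast.

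For process measures, such shifts could come from regional events or from drift in how a team scores records. For mortality only real regional shifts matter, because deaths come from registry linkage.

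The GEE clause governs all 14 models in Table 3. As written, nothing quantitative shows whether a claimed effect survives at the level that was randomised.

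**Working it through.** **Plan's own figures.** The intended record counts reproduce: 24 × 4 × 33 = 3168 and 24 × 4 × 60 = 5760. The nominal type I error is 0.05; sidedness is not stated, so two-sided is assumed. The planned 80% power was not reproduced, but the design matrix given to the software is not stated. That is a separate matter and is not used here.

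**Inputs from the documents.** Table 1 calendar (P0 at month 0; P1 at months 6–17, two hospitals per month; P2 = P1 + 9; P3 = P1 + 15); hospital intra-cluster correlation (ICC) 0.05; process 33 records per cell at 50%; mortality 60 records per cell at 15%.

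**Assumptions.** Teams are consecutive blocks of four in Table 1; cells are equal in size; shared team-by-period ICC is 0.005. That ICC means shifts with SD √(0.005 × 0.25) = 3.5 points for process and √(0.005 × 0.1275) = 2.5 points for mortality.

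**Hand check of the level problem.** Let s be the sampling variance of a hospital-period proportion and τ² the shared-shift variance, with shifts independent between periods and the four hospitals measured together. The true variance of a team-period mean is s/4 + τ². A hospital-level error counts only (s + τ²)/4.

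- Process: s = 0.25 × 0.95/33 = 0.00720 and τ² = 0.00125. True 0.00305, counted 0.00211, ratio 1.44, standard-error ratio 1.20.
- Mortality: s = 0.1275 × 0.95/60 = 0.00202 and τ² = 0.00064. True 0.00114, counted 0.00066, ratio 1.72, standard-error ratio 1.31.

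The uncorrected hospital test has simulated size 7.4% with no sharing (linear time), an effective critical value of 1.787. Dividing by 1.20 and 1.31 gives 1.487 and 1.362, so expected size is about 14% and 17%. The full simulation gives 13.5% and 16.1%.

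**Simulation.** Logistic GEE, exchangeable within hospital, no inspection effect, 6000 trials per setting (Monte Carlo standard error about 0.3 points near 5%). Entries are type I error in %, process / mortality, over linear, quadratic and cubic time:

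| Shared team-by-period shifts | Hospital, uncorrected z | Hospital, Mancl-DeRouen, t |
|---|---|---|
| None | 7–8 / 7–8 | 4–5 / 4–5 |
| ICC 0.005, correlated 0.98 per month | 8–9 / 9–10 | 5 / 6 |
| ICC 0.005, correlated 0.95 per month | 10–12 / 11–13 | 7 / 8 |
| ICC 0.005, independent between periods | 14–15 / 16–17 | 9–10 / 12 |

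The t reference has 24 − p degrees of freedom, with p the number of regression coefficients. With a four-knot cubic spline and no sharing, the uncorrected hospital test gives 8.1–9.0%. Across these and repeat runs with separate code, the ranges are about 6–9% (uncorrected, no sharing), 8–18% (uncorrected, ICC 0.005) and 6–13% (corrected, ICC 0.005; close to 5% in the mildest process case).

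**Team-by-period regression.** Take 6 × 4 = 24 cell log odds, with team fixed effects, exposure and time. Residual degrees of freedom are 24 − 6 − 1 − 1 = 16 for linear time, 15 for quadratic and 14 for cubic. Null rejection was 3–5.5% in every setting.

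**Is it the sharing that matters?** With hospital-by-period variation of ICC 0.01 that is not shared within teams, the corrected hospital test stays at 4.1–5.1%. So it is.

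**The case against.** **The level is not really ambiguous.** The power section and the GEE sentence both point to hospitals. This stands. A reader might infer that the robust error could equally be clustered on six teams, where an uncorrected z-test rejects 14–18% of the time with polynomial time. The documents do not imply that test, so the figure should not be held against the plan.

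**The cited method may include a correction.** This also stands. The 6–9% is what follows if none is used, not a demonstrated property of the analysis. The gap is that the plan does not say.

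**Shared shifts are hypothetical.** The documents give no size for them. For mortality, the assumed SD of 2.5 points is large beside the targeted fall of 3.5 points (15% to 11.5%). Common criteria, training, paired review and joint abstraction of P0 and P1 all limit team-specific scoring drift. A reader might infer that a corrected hospital-level test is known to be invalid; the documents do not support that. What remains is that hospitals are grouped by geography, P2 and P3 are abstracted at later separate audits by the same unmasked team, and the plan itself allows for other influences.

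**The team-level result need not govern.** The study calls itself quasi-experimental and specifies patient-level analysis. A reader might infer that a claim must rest on the team-level test alone. That is a defensible preference, but nothing in the documents requires it.

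**The focus groups cover context.** They may identify regional factors, but they do not change a standard error.

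**Conclusion.** The concern holds in two parts of different strength. First, the small-sample method is unstated. If none is used, type I error is about 6–9% with no shared shifts, which is a modest excess that an ordinary correction removes. This part needs no assumption about teams. Second, inference at hospital level sits below the randomised unit. If neighbouring hospitals share period-specific shifts, even the corrected hospital test can reject about 6–13% of the time at an assumed ICC of 0.005, while the team-by-period regression stays near 5%. This part depends on a shift size that the documents do not give, and it is worst when shifts are independent between periods.

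The change is worth making because the better analysis is cheap and uses the groups already randomised. It would not address a before/after scoring bias common to all teams, nor the low mortality power, which every test considered here shares.

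**What to change.** 1. State that the robust error is clustered on hospital.
2. Name a bias-corrected sandwich (Mancl-DeRouen or Kauermann-Carroll) with t on 24 − p degrees of freedom.
3. Add the analysis of 24 team-by-period values: cell log odds, or mean transformed length of stay, on exposure and time with team fixed effects and t on the residual degrees of freedom. To keep adjustment, use two stages. First regress the patient outcome on age, sex, organ dysfunction and hospital size (which the limitations section commits to including) plus 24 team-by-period indicators; then regress the 24 adjusted values. Simulated with one assumed binary covariate, and without hospital size, this version held 3.7–5.5%.
4. Report it beside the hospital-level result. Describe any effect significant only at hospital level as conditional on no shared team-by-period shifts.

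**Cost.** Wording and a few lines of code, no new data, and slightly wider intervals. Power with no team correlation, team regression against corrected hospital test: process 98 v 98% (linear) and 76 v 80% (cubic); mortality 41 v 45% and 22 v 23%. Allowing for spline time and repeat runs, the loss is up to about 5 points.

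**Alternative.** A reader might infer that every team-clustered sandwich is unsafe. That is too broad. A team-clustered Mancl-DeRouen variance with t on 5 degrees of freedom holds its level (about 3–5%), but process power falls to 84% (linear) and 45% (spline), against 97% and 72% for the corrected hospital test in the same runs. A version with only a 6/5 factor does not hold its level with cubic time (about 8%) or spline time (9–10%).

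**Dating.** This version is dated November 2021, after the collection scheduled in Table 1 ends in mid-2018. Label the added analysis with the date it was specified.
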